1 BACKGROUND

Healthcare-associated transmission of NTM

Pulmonary nontuberculous mycobacteria (NTM) infection is recognized as one of the most challenging infections to treat among cystic fibrosis (CF) patients, notable for prolonged treatment courses and often poor response to therapy.^{1,2} Positive cultures for NTM occur in about 20% of children and adults with CF.³ However, the source of NTM infection, modes of transmission, and exposure risks are poorly understood. It is thought that NTM is primarily acquired from environmental sites including soil and water as well as water supply systems to homes, hospitals, and clinics and from aerosols generated by flowing water from taps, showers, and fountains.⁴⁻⁶ Nonetheless, no direct molecular link has been established between environmental NTM and respiratory CF NTM.⁷ Healthcare-associated transmission of NTM among CF patients has been suspected⁸⁻¹⁰ and is of growing concern for CF Centers worldwide. Bryant *et al.* reported widespread global transmission of NTM, potentially via person-to-person transmission of fomites and aerosols,¹¹ but no standardized epidemiologic investigation tool for healthcare-associated NTM acquisition has been published.

[figure not shown]
CO-RDP serves as a national reference laboratory for CF NTM

The Colorado Research Development Program (CO-RDP) provides a national reference laboratory for CF NTM.¹² NTM respiratory isolates received from CF Care Centers around the U.S. undergo culture, molecular identification, antimicrobial susceptibility, and whole genome sequencing (WGS).¹³ Using this approach, the CO-RDP has identified clusters of NTM isolates, defined as highly similar strains at the genomic level, harbored by two or more CF patients who are cared for at the same CF Care Center. These identifications have heightened our concern for potential healthcare-associated NTM acquisition originating from patient-to-patient transmission or a common environmental source within Centers.

Identification of highly similar clusters of NTM within the care center network

Analysis of the 2016 CF Foundation (CFF) Patient Registry Annual Data Report found 20% of patients cultured for NTM between 2012-2016 had a NTM species isolated at least once.¹⁷ In 2017, of the 15,041 CF patients in the national registry who had an NTM culture performed that year, 1,903 (12.7%) had an NTM species isolated one or more times.¹⁸ The modes of acquisition of NTM in CF remain unclear (**Figure 1**).

The CO-RDP comprises multiple coordinated cores which receive, bank, culture, sequence, and analyze NTM clinical isolates from CF clinics around the U.S. Extracted NTM DNA from received samples is sequenced via WGS and analyzed for phylogenetic relatedness. As of January 2019, 123 facilities across the nation have submitted CF NTM isolates that have been sequenced. Phylogenetic data of NTM isolates from CF patients in the U.S. (**Figure 2**), as well as reference and environmental stains worldwide, are being collected in an ongoing fashion by the CO-RDP, and we found that highly similar NTM strains are shared within individual Care Centers (**Figure 3**) as well as between geographically

distant Centers. This work is clinically significant because a shared highly similar strain within a healthcare setting suggests common environmental sources of acquisition or patient- to-patient transmission.⁹

To define relatedness, the CO-RDP has examined the range of single-nucleotide polymorphism (SNP) differences among isolates from different patients compared to longitudinal isolates from the same patients over time to establish an evidence-based SNP threshold that is consistent with a clonal or highly similar strain within each NTM species.^{13,19} As this genomic database expands, thresholds of similarity will be refined through continued acquisition of longitudinal isolates collected from patients. Together, the inter- and intra-patient information defines a threshold to initiate an epidemiologic investigation. As the number of SNPs between strains increases, the likelihood of shared origin decreases. SNP threshold numbers are also dependent on the size of the core genome used to assess similarity. The CO-RDP utilizes WGS and phylogenomic analysis to examine the population structure and diversity of each NTM species and subspecies, and to identify clustered strains that are phylogenetically-related and nearly identical at the core genome level. Using the CO-RDP data driven methodology, a threshold of 15 SNP for *M. abscessus* ssp. *abscessus* (MAB) is stringent, reliable and provides an optimal approach to assess similarity between isolates.^{13,19}

[figure not shown]

Figure 2: CF NTM isolates sequenced by the CO-RDP.

[figure not shown]

Figure 3: CO-RDP identified NTM clusters within 10 CF Care Centers.

Multiple reports concerning healthcare associated outbreaks of NTM among CF patients continue to appear in the literature.⁸⁻¹⁰ Despite the reports, no standardized approach to epidemiologic investigation has been established for examination of healthcare-associated CF NTM outbreaks. Criteria must be met to validate NTM disease transmission.²⁰ NTM bacterial isolates must be genetically-matched between the patient and environment or between patients. Evidence of epidemiologic exposure and potential cross-infection must exist. Currently, **WGS is the gold standard for NTM isolate comparison** and was used in the study at Papworth Hospital to assess transmission of NTM between CF patients.⁹ The authors examined WGS on 168 consecutive isolates of *M. abscessus* from 31 adult CF patients in a Center from 2007-2011. Using core genome SNP analysis, they identified highly similar (<25 SNP) clusters of *M. abscessus massiliense* (MMAS) isolates from patients who demonstrated opportunities for cross- infection via overlapping clinic visits using epidemiological data and contact investigation. The authors concluded substantial evidence existed to support **healthcare-acquired transmission**. One smaller study utilized a similar approach to evaluate highly similar NTM isolates, but the data did not support healthcare-associated transmission of infection.²¹

1.1 Overview of Non-Clinical Studies

Not Applicable

1.2 Overview of Preliminary Studies

When the CO-RDP receives NTM clinical isolates from around the U.S., DNA is sequenced via WGS and analyzed for genetic relatedness at the core genome level. Mycobacterial DNA is sequenced using Illumina MiSeq 2X300 chemistry. Sequence reads are mapped to the appropriate mycobacterial reference genome and compared to find phylogenomic differences at the SNP level. As of January 2019, over 1,000 CF NTM isolates from 631 patients at 92 contributing facilities have *been banked*. To date, 904 CF NTM isolates *have been sequenced from 79 U.S. Care Centers, representing a total of 13 predominant NTM species and subspecies (Figure 2)*. To determine a threshold of genetic similarity for highly similar isolates, pairwise SNP distances in the core genome were calculated between all pairs of “same” (within-patient) or “different” (between-patient) isolates. We observed that 25 or fewer SNPs define background similarity of same-patient isolates for MAB and MMAS. Thus, a conservative threshold of 15 SNPs was chosen to define genetic clusters between patients, representing likely transmission events or shared source acquisition.

Findings: Unpublished data from the CO-RDP of 114 isolates from CF MAB patients across the country demonstrates 26 of 114 (23%) had isolates in highly related clusters. *Twelve of 114 (11%) had isolates in clusters and received care in the same Center. Clusters are occurring among multiple *M. abscessus* subspecies as well as *Mycobacterium avium* complex (MAC) subspecies.*

Preliminary results from one Care Center utilizing the HALT NTM toolkit investigated six clusters of patients with highly similar respiratory NTM isolates, including *M. abscessus* and MAC. The size of the highly related clusters ranged from 2-3 patients. Among the six identified NTM clusters, two clusters occurred with MAB, one with MMAS, *two with *M. avium* (MAV), and one with *M. intracellulare**. No patients within a cluster are related or living together. This is the first description of a MAC cluster.

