PARTICIPANT SELECTION CRITERIA: Inclusion Criteria	
PART A / Epidemiologic Investigation: Inclusion Criteria:
 
 1. Written informed consent is not required for this retrospective epidemiological study. 2. Diagnosis of CF consistent with the 2017 CFF guidelines. 3. Male or female participant of any age who have a history of NTM species or sub-species collected from expectorated sputum, induced sputum and/or bronchoalveolar lavage and identified by the CO-RDP as falling into a highly-related cluster within a single CF Care Center. 4. Controls subjects are male or female participants of any age who have a history of NTM species or sub-species collected from expectorated sputum, induced sputum and/or bronchoalveolar lavage and identified by the CO-RDP as NOT falling into a highly-related cluster within a single CF Care Center. 
PART B / Water Biofilm Collection: Inclusion Criteria: N/A

PARTICIPANT SELECTION CRITERIA: Exclusion Criteria	
PART A / Epidemiologic Investigation: N/A
 
PART B / Water Biofilm Collection: N/A

CONCOMITANT MEDICATIONS	
Allowed: N/A Prohibited: N/A

PRIMARY ENDPOINT	
PART A / Epidemiologic Investigation: Identification of a shared healthcare-associated source(s) between patients in a CF Care Center.
 
PART B / Water Biofilm Collection:

	Identification of biofilm isolates that are highly related to the isolates recovered from patients.
SECONDARY ENDPOINTS	
PART A / Epidemiologic Investigation: The secondary endpoints are:
 
 ▪ Incidence and prevalence of CF NTM species/subspecies by geographical region. 
PART B/ Water Biofilm Collection: The secondary endpoints are:
 
 ▪ Incidence and prevalence of healthcare-associated water biofilm NTM species/subspecies by geographical region.
EXPLORATORY EVALUATIONS	None
PLANNED INTERIM ANALYSIS	No formal interim analysis involving a data monitoring committee (DMC) is planned.

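### The control definition has no buffer above the 15-SNP cluster cut, so possibly related same-Center pairs at 16 to 25 SNPs can enter the comparison group and pull the dichotomised tests towards no difference

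*Protocol*

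**What the plan says.** Section 1.2 of the protocol compares pairwise core-genome distances within and between patients. It reports: "We observed that 25 or fewer SNPs define background similarity of same-patient isolates for MAB and MMAS". It then sets the working cut for clusters: "Thus, a conservative threshold of 15 SNPs was chosen to define genetic clusters between patients".

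Section 1 says that for MAB this cut "is stringent, reliable and provides an optimal approach to assess similarity between isolates". It also says that "thresholds of similarity will be refined through continued acquisition of longitudinal isolates collected from patients", and describes a gradient: "As the number of SNPs between strains increases, the likelihood of shared origin decreases".

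Controls are defined in the synopsis, inclusion criterion 4, as NTM-positive patients "identified by the CO-RDP as NOT falling into a highly-related cluster within a single CF Care Center". The exclusion criteria, in the synopsis and in section 6.3, are not applicable. Section 4.1 has the CO-RDP identify two controls per clustered subject. The discussion just before section 2 expects control pairs to capture the background frequency of overlap that has nothing to do with transmission.

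Section 15.1 and the primary-endpoint analysis compare pairs with similar and dissimilar strains by t-tests and by logistic regression. They also plan a linear regression on strain similarity as a continuous quantity. No SNP value is attached to dissimilar.

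**The concern.** A strict cut is conservative for calling a cluster because it keeps doubtful pairs out of the case group. Here those pairs have only one other place to go, the comparison group, and for that group the same cut is lenient. Two patients at one Center whose MAB isolates differ by 20 SNPs are as close as isolates from a single patient can be on the protocol's own figures, yet both may serve as controls.

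If some such pairs do share a source, they bring transmission-related overlap into the group meant to show overlap without transmission. The contrast then shrinks, and a weak or null result could be read as evidence that healthcare overlap does not matter. Section 15.6 ties the sample size to the clusters found, so lost power cannot readily be recovered by adding cases.

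**Working it through.** **What can be reproduced.** Section 1.2 reports 26 of 114 patients in highly related clusters: 26/114 = 22.8%, stated as 23%. It reports 12 of 114 in clusters with care at the same Center: 12/114 = 10.5%, stated as 11%. Both agree. The 15-SNP cut itself cannot be re-derived, because the within-patient and between-patient distance distributions are not in the text.

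**The gap, side by side.**

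| Item | Value | Place |
|---|---|---|
| Same-patient range, MAB and MMAS | 25 SNPs or fewer | section 1.2 |
| Between-patient cluster cut | 15 SNPs | section 1.2 |
| Control rule | not in such a cluster; no minimum distance | synopsis, inclusion criterion 4 |
| Exclusion criteria | not applicable | synopsis; section 6.3 |

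Reading the cut as 15 or fewer, distances of 16 to 25 SNPs lie inside the same-patient range and outside the cluster definition. Nothing in the control rule keeps them out.

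**Effect on the contrast.** Let p1 be the overlap rate in truly related pairs, p0 the rate in truly unrelated pairs, and f the truly related share of the comparison pairs. Then:

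- observed comparison rate: pc = (1 − f) × p0 + f × p1
- observed difference: p1 − pc = (1 − f) × (p1 − p0)
- required sample size: rises by roughly 1/(1 − f)²

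Only truly related pairs count towards f, so f cannot exceed the share of comparison pairs at 16 to 25 SNPs from this source.

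**Illustration.** The documents give neither overlap rates nor f, so these are assumptions: p1 = 0.60, p0 = 0.30, two comparison pairs per similar pair, two-sided alpha 0.05. For example, at f = 10%, pc = 0.9 × 0.30 + 0.1 × 0.60 = 0.33, and the odds ratio is (0.60/0.40)/(0.33/0.67) = 3.05.

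| f | pc | Difference | Odds ratio | 1/(1 − f)² | Similar pairs for 80% power | Power with 40 similar pairs |
|---|---|---|---|---|---|---|
| 0 | 0.300 | 0.300 | 3.50 | 1.00 | 31 | 0.89 |
| 5% | 0.315 | 0.285 | 3.26 | 1.11 | 35 | 0.85 |
| 10% | 0.330 | 0.270 | 3.05 | 1.23 | 39 | 0.81 |
| 20% | 0.360 | 0.240 | 2.67 | 1.56 | 50 | 0.71 |
| 30% | 0.390 | 0.210 | 2.35 | 2.04 | 66 | 0.59 |

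With p0 = 0.20, f = 10% takes the odds ratio from 6.00 to 4.75. With p0 = 0.40, it goes from 2.25 to 2.07. Whenever p1 exceeds p0 the shift is towards no difference. The sample sizes and powers treat pairs as independent. Pairs that share a patient are not, so real power would differ.

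**The case against.** **The size is unknown.** No count of 16 to 25 SNP pairs is given, and f may be near zero. No species matching of controls is stated, and section 1.2 lists 13 predominant species and subspecies. Unmatched controls would often be of another species and could not fall in this band. This stands, and it limits the point to a possible bias. A reader might infer that the control group is contaminated and the effect diluted as a matter of fact; the protocol does not show that.

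**A same-patient range is not proof of relatedness between patients.** Section 1 presents the 15-SNP cut as data-driven for MAB and says that shared origin becomes less likely as distance grows. This also stands, so such pairs are indeterminate rather than missed cases. But a gradient has no break at 15 SNPs, which argues for a middle band.

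**The cited hospital study.** A reader might infer that anyone 16 to 25 SNPs from another patient would have been a cluster member there. Section 1 says only that "they identified highly similar (<25 SNP) clusters of" one subspecies, MMAS. Its limit excludes 25 itself, and section 1 notes that thresholds depend on the size of the core genome, so the figure does not carry over to another pipeline.

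**Pairs and patients.** That a 16 to 25 SNP pair counts as dissimilar is an inference. The control rule classifies patients, the statistical section gives no SNP value, and no linkage rule is stated, so two patients more than 15 SNPs apart might still share a cluster through a third. Other pairs in the band remain eligible.

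**An analysis without the cut is already planned.** The linear regression enters a 20-SNP pair as 20 SNPs, so it is wrong to infer that every analysis is biased. Only the dichotomised tests and the logistic regression are exposed.

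**Detail for the SAP.** A middle band and a sensitivity run could be placed there, and the SAP is not at hand. The control rule is different: it is a protocol selection rule that decides whose records are abstracted. An SAP could later drop near-threshold controls, but only by losing data already collected.

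**Conclusion.** The point holds as a weakness in a stated selection rule. The control definition is the plain complement of a strict cluster definition, although the protocol's own data put same-patient MAB and MMAS isolates up to 25 SNPs apart. Possibly related same-Center pairs can therefore enter the comparison group. Any resulting bias is towards no difference and multiplies the risk difference by (1 − f). It is minor if f is 5% or less and material from about 20%. Those magnitudes rest on assumed overlap rates, an assumed f, and related comparison pairs overlapping as often as clustered pairs do.

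The 25-SNP figure covers MAB and MMAS only. The protocol gives none for MAC, which accounts for three of the six clusters in the preliminary single-Center work. Section 15.1.1 limits all analyses to clustered subjects, which conflicts with having controls. That must be reconciled separately and does not remove this point. The change is worth making because it is cheap and protects the contrast that the controls exist to provide.

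**What to change.** 1. Keep 15 SNPs as the cut for cases.
2. For MAB and MMAS, select as controls only patients whose isolates are more than 25 SNPs from every isolate of any *other* patient at that Center. The words on other patients are needed; otherwise a control's own repeat isolates would rule that control out.
3. Judge dissimilarity pair by pair: more than 25 SNPs between the two patients' isolates. Clustered patients can then still form dissimilar pairs across different clusters.
4. Report pairs at 16 to 25 SNPs as a separate indeterminate band.
5. Add one sensitivity analysis of the dichotomised comparisons with 25 SNPs as the cut.
6. For MAC, apply the corresponding same-patient limit from the CO-RDP data and state it in the protocol.

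The cost is a slightly smaller control pool and one extra analysis. For MAB and MMAS, section 1.2 indicates that the CO-RDP already calculates the pairwise distances this needs.

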Discussion: Martiniano *et. al.* evaluated the clinical significance of a first positive CF NTM culture and reported subjects that develop active NTM disease have a lower baseline forced expiratory volume in 1 second (FEV₁) at the time of first positive culture and an increased rate of decline in FEV₁ one year preceding the first positive culture.³⁶ ***The finding of accelerated lung function decline in patients with NTM disease before the time of first positive culture strongly suggests the presence of respiratory NTM in CF patients for a year or more before initial clinical detection.*** Based on that knowledge, the timeline for biologically plausible acquisition prior to detection is reasonably estimated to be 1-2 years. For this reason, the abstraction timeframe in the HALT NTM toolkit timeframe begins 2 years prior to the first positive culture of the patient with the longest period of time with NTM+ culture. The timeframe ends when the second paired patient has a first positive culture. This approach to setting the timeline for data

abstraction ensures plausible directionality of transmission and allows for a 1-2 year timespan from NTM acquisition to NTM culture positivity.


In this study, we are unable to exclude NTM acquisition from direct patient-to-patient contact or via a common environmental source outside the healthcare setting. Evaluation of non-healthcare settings is beyond the scope of this project, but serves as a potential future area of investigation. There may also be a baseline frequency of patient overlap that is not related to transmission events in the healthcare setting that we expect to capture with evaluation of control pairs of subjects. Despite this small sample size, this preliminary data provides insight into the frequency and nature of patient overlap in the healthcare setting and reveals that among CF patients receiving healthcare in the same location, there are opportunities for close direct or indirect contact. In the setting of strict IP&C measures with single patient rooms, healthcare staff gowning and gloving, patients wearing masks, aggressive cleaning procedures between patients, and maintenance of patient-to-patient separation of 6 feet or more, direct and indirect patient overlap should be minimized. However, incidental or unanticipated contacts remain a risk. If patients in fact have no direct or indirect contact, *investigation of the healthcare environment is essential to eliminate a common healthcare-associated environmental source as the point of CF patient NTM acquisition*.

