4 STUDY DESIGN

4.1 Study Overview

PART A / Epidemiologic Investigation:

This study will retrospectively review and collect data from patients with CF and culture positive for an NTM isolate falling in a highly-related cluster, identified by the CO-RDP, within a single CF Care Center. Two control subjects will be identified by the CO-RDP for every subject falling within a cluster. Retrospective epidemiologic data collection and input into REDCap is detailed (**Appendix 1 and 2**). Up to 20 Care Centers will be offered enrollment.

PART B / Water Biofilm Collection:

This study will also collect and analyze water biofilms from a variety of water sources in the healthcare setting including sink faucets, showerheads, shower hoses, ice machines, drinking fountains, and decorative water features. Environmental sampling instructions are detailed (**Appendix 3**).

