15 STATISTICAL METHODS AND CONSIDERATIONS

15.1 General Considerations

For each of the primary and secondary outcomes, biostatistical analysis of the multicenter data will be completed using both qualitative and quantitative approaches. We will identify a set of variables used to assess degree of proximity of subjects in time and/or space. For example, two subjects with neighboring rooms at a hospital would have close proximity, but proximity would be increased for two subjects at a facility that had longer overlap time, relative to a pair of subjects that had shorter overlap. We will explore creating composite measures of quantitative proximity that incorporate multiple variables. Qualitative measures of proximity, such as location type (testing laboratory, patient room) will also be assessed. Several testing approaches will be used to compare the relationship between similarity of strains and degree of proximity of subjects. In the simplest form, descriptive statistics will be computed for proximity variables, for pairs of subjects who are determined to have similar strains versus those who have dissimilar strains, and multivariate or 2-sample t-tests will be performed to test for differences between these groups. More advanced modeling will be performed to determine the relationship between the degree of similarity in strains with the proximity and subject characteristic variables; multiple linear regression will be used when considering continuous strain similarity, while multiple logistic regression will be used when considering subjects with dichotomized (similar/dissimilar) strains to other subjects.

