15.1.1 Data Sets Analyzed

All analyses will be based on the group of subjects that are identified by the CO-RDP as having NTM isolates, defined as highly similar strains at the genomic level, harbored by two or more patients within a single Care Center.

152 Demographic and Baseline Characteristics

The following baseline demographic and clinical characteristics will be reported: age, gender, race, ethnicity, zip code, and NTM sub/species.

153 Analysis of Primary Endpoint

PART A / Epidemiologic Investigation:

The primary endpoint will characterize the origins and prevalence of healthcare-associated patient-to-patient transmission of NTM among different CF Care Centers. We will further characterize the source(s) of direct or indirect transmission of NTM within an individual CF healthcare setting. We will identify a set of variables used to assess degree of proximity of subjects in time and/or space. For example, two subjects with neighboring rooms at a hospital would have close proximity, but proximity would be increased for two subjects at a facility that had longer overlap time, relative to a pair of subjects that had shorter overlap. We will explore creating composite measures of quantitative proximity that incorporate multiple variables. Qualitative measures of proximity, such as location type (testing laboratory, patient room) will also be assessed. Several testing approaches will be used to compare the relationship between similarity of strains and degree of proximity of subjects. In the simplest form, descriptive statistics will be computed for proximity variables, for pairs of subjects who are determined to have similar strains versus those who have dissimilar strains, and multivariate or 2-sample t-tests will be performed to test for differences between these groups. More advanced modeling will be performed to determine the relationship between the degree of similarity in strains with the proximity and subject characteristic variables; multiple linear regression will be used when considering continuous strain similarity, while multiple logistic regression will be used when considering subjects with dichotomized (similar/dissimilar) strains to other subjects.

PART B / Water Biofilm Collection:

The primary endpoint will characterize clinically-relevant NTM found in water biofilms within CF healthcare settings and determine if the biofilm isolates are highly related to isolates recovered from patients.

154 Analysis of Secondary Endpoints

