15.6 Sample Size

Up to 20 CF Care Centers are eligible for enrollment. Sample size will be determined based on CO-RDP WGS finding of highly related NTM species and subspecies among patients receiving care at an individual CF Care Center.

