APPENDIX 2 REDCAP USER GUIDE

So, you've received a letter from National Jewish Health Advanced Diagnostic Laboratories (NJH ADx) saying you have patients at your center with a highly similar strain of NTM. Now what?

1. Contact [name] at NJH. She will help you with initial questions regarding study design and study start-up, including IRB and database requirements.
2. For NJH REDCap access, you will be sent a link to complete REDCap training. You will be asked the following:
 - For the question "Are you an employee of National Jewish Health?" select No.
 - Explain your affiliation as "HALT NTM"
 - National Jewish Health Sponsor is "[name]"
 - For department, indicate your CF center/institution name.
 - Complete the rest as indicated.
 - Email [name] or [name] once you've been given access so you can be added to the project.
3. Now you have access to the database. Log on to REDCap. On the welcome screen, open the HALT NTM project.
4. On the left hand side under Applications, open the File Repository. Download the HALT NTM cheat sheet.
5. Print a HALT NTM cheat sheet for each unique pair:
 - If there are two patients listed on your letter, you will have one unique pair.
 - If there are three patients listed on your letter, you will have three unique pairs.
 - If there are four patients listed on your letter, you will have six unique pairs.
 - This is because the date ranges are compared between two subjects and is unique for each pair.
6. Complete the first six lines on the HALT NTM cheat sheet for each unique pair. You will need to refer to it during pairing and data extraction.
7. Back in REDCap, on the left hand side under Data Collection, click Add / Edit Records. On the Add/Edit Records page, click on the button Add new record. You will be taken to the Record Home Page. There will be a NEW Study ID XXX-XX. Record that number (XXX-XX) on the HALT NTM cheat sheet. It is auto-generated by REDCap. You will need it later.
8. The first Form to complete is Demographics. Open the form by clicking on the circle under Demographics. Near the top of the form under the header **Pairs Survey** is a link to the "**Finding Pairs survey**." Click on the link. You will be taken to an interactive tool that will help you determine if this subject is "subject 1" or "subject 2" in this pairing.

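### Part A describes its comparison pairs in two unlinked ways and leaves controls out of the analysis set, so the background overlap rate depends on an unstated mix of pairs

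*Protocol*

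**What the plan says.** In the discussion under Protocol Section 1.2, some overlap is accepted as unrelated to transmission, a background "that we expect to capture with evaluation of control pairs of subjects". Section 4.1 provides for the controls: "Two control subjects will be identified by the CO-RDP for every subject falling within a cluster". The synopsis repeats the ratio and defines controls as NTM-positive patients "identified by the CO-RDP as NOT falling into a highly-related cluster within a single CF Care Center". It does not require the same Center, species or period.

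The analysis text does not take up these terms. The synopsis statistics row, Section 15.1 and Section 15.3 (Part A) describe proximity "for pairs of subjects who are determined to have similar strains versus those who have dissimilar strains", followed by t-tests and then linear or logistic regression. None of the three mentions controls, limits the pairs to one Center or separates kinds of dissimilar pair. Section 15.1.1 opens: "All analyses will be based on the group of subjects that are identified by the CO-RDP as having NTM isolates". The rest of that sentence narrows the group to patients sharing highly similar strains at a single Center.

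Appendix 2 gives a pairing rule only for patients named on the cluster letter, for example: "If there are four patients listed on your letter, you will have six unique pairs". The available text does not say how a control pair is formed.

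**The concern.** The similar-versus-dissimilar contrast is how Part A separates overlap that may reflect a shared source from overlap that any two patients of a Center would have. Its reference group decides the answer.

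Call a clustered patient a case. A similar pair holds two cases, a control-control pair none, a case-control pair one, and a pair of cases from different clusters two. Anything about a patient that changes overlap with everyone (inpatient days, paediatric or adult service, calendar period) enters these types in different amounts. If they are pooled, the reference frequency depends on how many controls and clusters each Center contributes. If 15.1.1 is followed to the letter, the only dissimilar pairs are cases from other clusters or other Centers.

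A later SAP may not fully repair this, because abstraction is specific to the pair. Under Section 1.2 the window runs from two years before the earlier first positive culture to the other patient's first positive culture, and Appendix 2 has sites record only visits inside it. A pair type not planned at data collection may have no usable data. The window also lengthens with the gap between the two cultures, so opportunity to overlap can differ by pair type.

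**Working it through.** **Inputs from the protocol.** Pair rule (Appendix 2, step 5); two controls per case (Section 4.1); preliminary clusters, of which Section 1.2 says "The size of the highly related clusters ranged from 2-3 patients"; and Section 15.6: "Up to 20 CF Care Centers are eligible for enrollment". The protocol gives no overlap rate and no same-Center rule for controls. Controls at the same Center, and every rate below, are assumptions.

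**The plan's own figure.** k(k−1)/2 gives 1, 3 and 6 pairs for k = 2, 3 and 4, matching Appendix 2.

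**Pair counts at a one-cluster Center.** With k cases and 2k controls: similar = k(k−1)/2; control-control = 2k(2k−1)/2; case-control = k × 2k.

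| k | Similar | Control-control | Case-control | All dissimilar |
|---|---|---|---|---|
| 2 | 1 | 6 | 8 | 14 |
| 3 | 3 | 15 | 18 | 33 |
| 4 | 6 | 28 | 32 | 60 |

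Six clusters of 2 to 3 patients at one Center (13 to 17 cases) add 70 to 120 cross-cluster case pairs.

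**Section 15.1.1 read literally (cases only).** A one-cluster Center has 0 dissimilar pairs within the Center. Twenty Centers with one 2-patient cluster each have 40 × 39/2 − 20 = 760 dissimilar pairs, all between Centers.

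**Controls added, no Center restriction.** The same 20 Centers have 120 patients and 120 × 119/2 − 20 = 7,120 dissimilar pairs. Only 20 × 14 = 280 are within a Center, so 6,840/7,120 = 96% cross Centers. Suppose cross-Center pairs never overlap, and similar pairs and same-Center unrelated pairs both overlap 60% of the time. The within-Center difference is 0. The pooled reference is 0.6 × 280/7,120 = 2.4%, a difference of about 58 percentage points.

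**Pair mix within one Center.** Assume no transmission, a general tendency to overlap of 1 for a control and r for a case, and expected pair overlap equal to the product of the two. Similar pairs then have r². For k = 2 the expected ratios are:
- against control-control pairs: r²;
- against all dissimilar pairs: r²/[(6 + 8r)/14];
- against case-control pairs: r²/r = r;
- against cross-cluster case pairs: r²/r² = 1.

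| r | Control-control | All 14 dissimilar | Case-control |
|---|---|---|---|
| 0.8 | 0.64 | 0.72 | 0.80 |
| 1.0 | 1.00 | 1.00 | 1.00 |
| 1.25 | 1.56 | 1.37 | 1.25 |
| 1.5 | 2.25 | 1.75 | 1.50 |
| 2.0 | 4.00 | 2.55 | 2.00 |

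At r = 1.5 the middle entry is 2.25/(18/14) = 1.75; for k = 3 it is 2.25/[(15 + 27)/33] = 1.77.

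**Without the product model (k = 3).** Let similar pairs overlap 60% and control-control pairs 40%. Against control-control pairs the odds ratio is 1.5/0.667 = 2.25. If case-control overlap is 20%, 40% or 50%, the all-dissimilar reference is (15 × 0.4 + 18 × that rate)/33 = 29.1%, 40% or 45.5%, and the odds ratio is 3.66, 2.25 or 1.80. The two comparators agree when both pair types overlap equally often.

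**The case against.** A reader might infer that the protocol prescribes two incompatible comparators. The text does not go that far. Section 1.2 does not say that a control pair means control with control, and Sections 15.1 and 15.3 do not say that every dissimilar pair is used. Control pairs may well be the intended dissimilar pairs. The sentence in Section 1.2 is also a remark in a discussion of preliminary data, parts of that section were not available to me, and an unseen SAP may define the pairs. All of this stands, and it makes the fault a missing link, not a contradiction. It does not supply the definition, and it does not explain why 15.1.1 leaves out the controls.

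A second tempting reading is that the two sets carry different null hypotheses, or that control pairs always raise the risk of a false positive. Neither is supported. The t-test and regression null is no difference whichever set is used. The protocol gives no value of r, every ratio is 1.0 at r = 1, and the order reverses below 1.

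The planned regressions include patient characteristics and may remove part of the imbalance. They still need a defined set of pairs, and they adjust only for what is measured.

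Finally, comparing each case's similar pairs with that case's own dissimilar pairs is not a full cure. With 2-patient clusters and r = 1.5 it still gives 1.50 with one cluster at the Center, 2.25/[(8 × 1.5 + 2 × 2.25)/10] = 1.36 with two, and 2.25/[(24 × 1.5 + 10 × 2.25)/34] = 1.31 with six. A similar pair also belongs to both of its members and would be counted twice.

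**Conclusion.** The point holds as an unreconciled comparator. The protocol names control pairs as the source of background overlap, analyses similar against dissimilar pairs without linking the two, and states an analysis set without the controls it requires. Followed as written, the reference frequency rests on an unstated mix of pairs or, with cases only, on pairs from other clusters or Centers.

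The pair counts follow from the protocol's pair rule and 2:1 ratio once controls are taken to attend the same Center. The size of the shift is illustrative: at r = 1.5 with no transmission, the expected ratio runs from 1.5 to 2.25 according to the set chosen. Pooling across Centers could do more, if cross-Center pairs rarely overlap. The documents do not show which way the actual estimate would move, or that it would move at all.

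**What to change.** - Section 15.1.1: add the controls to the analysis set.
- Section 15.3: restrict the similar-versus-dissimilar contrast to pairs within the same Center. Under the synopsis definition, a same-Center pair that includes a control is then dissimilar by construction.
- Record pair type (case-control, control-control, cross-cluster case) as a variable. Report overlap for each type, and stratify or adjust by type so that types are never pooled unstratified. Keeping control-control pairs is useful: under the product assumption, the ratio of case-control to control-control overlap estimates r.
- Use the same terms in the Section 1.2 discussion and the synopsis.
- Optionally report the case-anchored contrast as a sensitivity analysis, stating that it lessens but does not remove the bias (when r differs from 1).

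The cost is wording, a pairing instruction for controls in Appendix 2 (including how the abstraction window is set for them), and somewhat wider intervals than an unstratified pooled comparison.
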